1.2 Protocol version

3.0

1.9 Participating Centres

All anaesthesia services and intensive care units of all European hospitals with cardiac surgery services will be invited to participate, most of them belonging to the Spanish group of renal dysfunction in cardiac surgery (GEDRCC2).

2. Background and current status of the issue

Acute *Kidney Injury* (AKI) is a major complication of cardiac surgery and its most severe forms are associated with significant morbidity and mortality^{[1][2]}.

Identification of patients at risk may facilitate early use of management protocols recommended by KDIGO (Kidney Disease: Improving Global Outcomes), such as haemodynamic and volume optimisation, monitoring of renal function and discontinuation or reduction of nephrotoxic drugs^{[3][4]}. The rate associated with cardiac surgery varies according to its different historical definitions, from 0.3% to 29.7%^{[5][6]}. Cases requiring renal replacement therapy (RRT) occur between 1.2%-3.0% in the studied cardiac surgery cohorts and their presence is an independent predictor of mortality.

Because AKI still lacks effective treatments in addition to support and elimination of the cause, early and specific diagnosis is an unmet but critical need for successful and personalised patient management. ^{[8][9][10]}

Creatinine, urea and urine output have been and are the main ways to diagnose and treat renal failure. Other types of biomarkers that seem to be related to risk of postoperative AKI are currently under study. Although more research is needed, they may eventually become predictive diagnostic tools. Several studies have indicated that the urinary level of NGAL^{[11][12]} excreted intraoperatively and after surgery is effective in predicting AKI in both adult and paediatric populations. Similar results have been obtained with other urinary biomarkers, such as the cell cycle arrest biomarkers TIMP-2 and IGFBP7^[11] KIM-1, NAG, IL-18 and L-FAP^[12]. The major limitation of these biomarkers is that they are not easily accessible in all hospitals and clinical settings. Recently Demirjian et al^[13] developed a predictive model in which they observed that perioperative change in serum creatinine and postoperative blood urea nitrogen, serum sodium, potassium, bicarbonate and albumin from the first metabolic panel after cardiac surgery show good predictive value for moderate to severe AKI within 72 hours and 14 days after the surgical procedure.

3. Hypothesis

The score developed by Demirjian et al has a good predictive ability for moderate to severe AKI after cardiac surgery in the European population.

4. Objectives

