4.1 Main

- Confirm the usefulness and externally validate the scale.
- Compare this scale with other models of AKI prediction after cardiac surgery: Thakar, Mehta, ISR, Callejas, Leicester, CRATE.

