4.2 Secondary

- Identify new risk factors for Acute Kidney Injury (AKI)
- Understanding the incidence of AKI after cardiac surgery in Europe
- Validating a model for predicting discharge dialysis after cardiac surgery
- Investigate the performance of these models in specific surgeries: coronary surgery without cardiopulmonary bypass and heart transplantation.
- Assess the performance of other scales and compare them.
- Determine the prevalence and risk factors for Acute Kidney Disease (AKD) (renal injury beyond 7 days, up to 90 days).
- Determine the prevalence and risk factors for new Chronic Kidney Disease (CKD) (follow-up for 120 days or 4 months).
- Determine the prevalence and risk factors for CKD progression, defined by a one-stage progression in patients with pre-existing CKD. Follow-up for 120 days (4 months).

5. Methodology

5.1 Design: descriptive, observational, prospective, multicentre, prospective study.

5.2 Study population: patients undergoing cardiac surgery.

5.3 Ethical aspects: the study has been approved for assessment by the Ethical Committee for Research with Medicines of the Principality of Asturias.

5.4 Inclusion criteria: All patients over 18 years of age undergoing cardiac surgery.

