5.6 Study variables

Hospital

Age

Sex

Male

Female

Race

Asian

Black

Multiracial

White

Weight (kg)

Height(cm)

BMI

Comorbidities

- Hypertension
- Insulin-dependent diabetes
- Non-insulin-dependent diabetes
- Congestive heart failure
- Coronary artery disease
- Triple Vessel coronary artery disease
- Chronic obstructive pulmonary disease
- Poor mobility (musculoskeletal, neurological)
- Chronic kidney disease
- Peripheral vascular disease
- Atrial fibrillation
- Liver disease

NYHA (New York Heart Association Functional Classification)

Left ventricular ejection fraction (LVEF) %

Pulmonary systolic pressure (mmHg)

Unstable angina

Recent miocardial infarction (90 days)

Smoker YES/NO/Ex-smoker

Receives iSGLT2 (dapagliflozin, canagliflozin, empagliflozin...)

Receives GLP1 agonists (liraglutide, semaglutide, dulaglutide...)

Receives calcium antagonists (verapamil, nifedipine, amlodipine...)

Preoperative values

Serum creatinine (mg/dL)

FGe by Cockroft-Gault mL/min/1.73 m²

FGe by EPI CKD ml/min

eGFR by MDRD ml/min/

Serum Albumin (mg/dL)

Serum Urea (mg/dL) or Serum BUN (mg/dL)

Serum sodium (mmol/L)

Serum potassium (mmol/L)

Serum bicarbonate (mmol/L)

Haemoglobin (mg/dL)

Platelets

Bilirubin (mg/dL)

Surgery

On-pump CABG

Off-pump CABG

Valvular

Aortic

Combined (coronary+valvular)

Other, multiple procedures (>2)

Heart transplant

Previous heart surgery

YES/NO

Euroscore II

Classification Surgery

- Emergent
- Urgent
- Elective
- Salvage (pre-operative cardiopulmonary resuscitation)

Catheter to surgery

- Within 24 h
- >24 h this admission
- >24 h previous admission
- No catheter prior to surgery

Pre-operative critical status (IABP, mechanical ventilation, VT, CRP, amines, renal failure)

YES/NO

Endocarditis at the time of surgery

YES/NO

Preoperative cardiogenic shock

YES/NO

Use of IABP prior to surgery

YES/NO

Intraoperative variables

- CPB (cardiopulmonary bypass) time min
- Aorta cross-clamp time (min)
- Vasopressors YES/NO
- Inotropes YES/NO
- Red blood cell transfusion YES/NO

Number of red cell concentrates transfused
Platelet transfusion YES/NO
Fresh Frozen Plasma Transfusion YES/NO
Intraoperative diuresis (ml)
Nadir hemoglobin (lowest intraoperative in mg/dL)
Antibiotic (Gentamicin, Vancomycin, Cefazolin...)

Immediate postoperative values

Time from end of surgery to first analytical panel (hours)
Serum creatinine (mg/dL)
Serum albumin (mg/dL)
Urea (mg/dL) or BUN (mg/dL)
Serum sodium (mmol/L)

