Serum potassium (mmol/L)
Serum chlorine (mmol/L)
Serum bicarbonate (mmol/L)
Lactate (mmol/L)

Urgent re-intervention first 24h

YES/NO

Length of hospital stay (days)

Discharge status

Discharge

Éxitus

Need for dialysis at discharge

YES/NO

Postoperative renal failure

Creatinine at ICU admission

Creatinine at 24h

Creatinine at 48h

Creatinine at 72h

Peak creatine 4th to 7th day

Peak creatine 7th to 14th day

Last creatinine at hospital discharge

Does the patient develops Stage 1 AKI in the first 14 days?

*Stage 1 AKI: (\uparrow) Creatinine 1.5-1.9 times baseline or ≥ 0.3 mg/dL increase

If yes, which day?

Does the patient develops Stage 2 AKI in the first 14 days?

*Stage 2 AKI: (\uparrow) Creatinine 2-2.9 times baseline

If yes, which day?

Does the patient develops severe AKI in the first 14 days?

* Stage 3 AKI : (\uparrow) Creatinine ≥ 3 times baseline or ≥ 4 mg/dL increase or dialysis.

If yes, which day?

Does the patient requires renal replacement therapy within the first 14 days?

If yes, which day?

5.7 Sample size estimation: Taking into account an incidence of moderate severe AKI in Spain of 9% according to previous studies and using the

Wilcoxon test, 1045 patients are needed to detect a difference of 0.1 in aROC with a power of 80% and an alpha error of 0.05. Assuming a 10% loss to follow-up, 1150 patients would be needed.

5.8 Data collection: a data collection notebook will be used to carry out the study. The researcher will include in it the sample of patients, without any data that would allow their identification.

5.9 Analysis of results: the results will be analysed using the statistical package IBM-SPSS 20.0 for Mac OS and RStudio version 1.1.463. The basic statistics of centralisation and dispersion will be used to describe the results. For comparison of means, t-tests for independent data or Mann-Whitney U-tests will be used in those cases where the conditions for their application are violated. Chi-square tests shall be used for comparison of proportions. Bonferroni correction shall be applied for multiple contrasts. To study the predictive ability, 2 measures will be studied, the discrimination ability by means of the area under the ROC curve and the calibration by means of the Hosmer Lemeshow Test. The areas under the ROC curve will be compared using the Mann-Whitney U test.

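### Without creatinine change alone as a comparator, a good AUC for the score cannot by itself support the usefulness part of main objective 1

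*Combined protocol and SAP*

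**What the plan says.** - **Index score (section 2).** Its inputs are "perioperative change in serum creatinine and postoperative blood urea nitrogen, serum sodium, potassium, bicarbonate and albumin from the first metabolic panel after cardiac surgery". It is reported to have "good predictive value for moderate to severe AKI within 72 hours and 14 days after the surgical procedure".
- **Outcome (5.6, postoperative renal failure).** Stage 2 is "Creatinine 2-2.9 times baseline". Stage 3 is "Creatinine ≥ 3 times baseline or ≥ 4 mg/dL increase or dialysis". No urine-output criterion is listed. The list of creatinine values under this heading starts with "Creatinine at ICU admission".
- **Objectives and comparators.** The first main objective (4.1) is to confirm the usefulness of the scale and to validate it externally. The second is to "Compare this scale with other models of AKI prediction after cardiac surgery: Thakar, Mehta, ISR, Callejas, Leicester, CRATE". A secondary objective (4.2) is to "Assess the performance of other scales and compare them", with no scale named.
- **Analysis (5.9).** Performance is judged by the area under the ROC curve and the Hosmer-Lemeshow test. Areas are to be compared with the Mann-Whitney U test.
- **Data (5.6).** Serum creatinine is collected both before surgery and in the immediate postoperative panel.

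**The concern.** One of the six inputs is an early reading of the quantity that, measured over the following days, mainly determines the outcome. Some discrimination is therefore expected from that input alone. Section 2 itself names creatinine among the main ways in which renal failure is diagnosed and treated, so the change from the preoperative value to the first panel is information the clinical team already holds.

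The plan does not set the score against that simple benchmark. If the score reaches a good AUC, the reader will not know whether urea, sodium, potassium, bicarbonate and albumin contributed to it or whether the creatinine term did the work. At stake is the usefulness conclusion: whether computing the score offers anything beyond a subtraction of two values already on the chart.

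**Working it through.** **1. Is the benchmark anywhere in the plan?** Section 4.1 names six published models, 4.2 refers to unspecified other scales, and 5.9 gives AUC and Hosmer-Lemeshow. None names creatinine change alone, a score without creatinine, or an analysis of incremental value.

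**2. Could creatinine alone give a good AUC?** From the plan: 9% incidence (5.7). Assumed: the early and the later log creatinine ratio, X and Y, are standard bivariate normal with correlation r, and the event is the top 9% of Y. The threshold is then t = Φ⁻¹(0.91) = 1.341, and

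AUC = ∫ f₁(x) F₀(x) dx,

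where f₁(x) = φ(x) Φ((rx − t)/√(1 − r²))/0.09 is the density of X in events, and F₀ is the distribution function of X in non-events.

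| Assumed r | AUC, creatinine change alone | AUC, creatinine change plus pure noise |
|---|---|---|
| 0.1 | 0.56 | – |
| 0.2 | 0.61 | – |
| 0.3 | 0.67 | – |
| 0.4 | 0.72 | 0.72 |
| 0.5 | 0.77 | 0.77 |
| 0.6 | 0.83 | 0.82 |
| 0.7 | 0.875 | 0.87 |

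The last column represents a score whose other five analytes carry no information (noise SD 0.2 times that of the creatinine term). From r of about 0.5 upwards, such a score would still have an AUC of 0.77 or more. At r of 0.3 or less it would not look good, and a high AUC for the full score would then point to a contribution from the other analytes.

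**3. The plan's own sample size.** Section 5.7 gives 1045 patients for an AUC difference of 0.1 at 80% power and alpha 0.05. It does not state the reference AUC, the correlation between scores or the sidedness, so the figure cannot be uniquely reproduced. Some combinations come close (two AUCs, 0.70 against 0.80, correlation 0.3, binormal variance, two-sided: 1048). The point here does not depend on it.

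**4. Can that sample carry the added comparison?** Events: 0.09 × 1045 = 94.05; non-events: 950.95. The Hanley-McNeil variance is

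Var(A) = [A(1 − A) + (n₁ − 1)(a − A²) + (n₀ − 1)(b − A²)]/(n₁n₀), with a = A/(2 − A) and b = 2A²/(1 + A).

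For A = 0.70: [0.21 + 93.05 × 0.0485 + 949.95 × 0.0865]/(94.05 × 950.95) = 86.9/89,437 = 0.00097, so SE = 0.0312. The detectable difference for paired AUCs solves d = 1.96·SE₀ + 0.842·SE₁, with SE₀ the standard error of the difference under no difference and SE₁ that under d:

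- A = 0.70, correlation between AUCs 0.5: 1.96 × 0.0312 + 0.842 × 0.0300 ≈ 0.086.
- A = 0.85, correlation 0.9: 1.96 × 0.0113 + 0.842 × 0.0111 ≈ 0.031.

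Over an assumed AUC of 0.70-0.85 for creatinine alone and an assumed correlation of 0.5-0.9, the range is about 0.03 to 0.09, inside the 0.1 that the plan uses.

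**5. Power by simulation** (paired DeLong test, two-sided 0.05, no Bonferroni adjustment, r = 0.5 or 0.6, 600 runs per scenario):

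| True gain in AUC | Power |
|---|---|
| 0.004-0.006 | 16-18% |
| 0.016-0.019 | 43-50% |
| 0.035-0.043 | 83-84% |
| 0.060-0.073 | 99% |

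**The case against.** The strongest reply is that the plan does not claim what is being asked of it. Section 3 states only that the published score predicts well in a European population. Validation tests a score as a whole, and separating its components is a different question. This stands: external validation and the six-model comparison need no extra comparator to be sound. What it does not cover is the usefulness wording in 4.1, which goes beyond validation and is not defined.

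Stronger readings are tempting, and the documents do not support them:

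- **That the study cannot show the score adds anything.** It can show gain over the six named models.
- **That the six models all lack postoperative creatinine, so that any advantage comes only from reading creatinine later.** The documents do not list their inputs.
- **That the study will recommend adopting the score.** No section commits to that.
- **That predictor and outcome share a measurement.** The outcome list begins at ICU admission, baseline is not defined, and no rule starts the outcome window after the index panel. Overlap therefore cannot be excluded, but it is not stated either.
- **That the outcome is nothing but a multiple of baseline.** Stage 3 can also be reached through an absolute rise or dialysis.

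It is also fair to say that the AUC figures come from assumed correlations. They are not evidence about this cohort.

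**Conclusion.** The point holds, limited to the usefulness part of main objective 1. The score contains the perioperative creatinine change, the outcome is defined mainly by creatinine, and creatinine change alone is not a comparator. A good AUC is therefore compatible with no contribution from the other five analytes, and by itself it cannot support value beyond the creatinine change already available.

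The size is a possibility, not a forecast: about 0.72 to 0.875 for creatinine alone at correlations of 0.4 to 0.7, and about 0.56 to 0.67 at 0.1 to 0.3. This rests on the bivariate-normal model and the 9% incidence, and on taking moderate-to-severe AKI to mean Stages 2 and 3. The logical gap does not depend on the correlation; how much it matters in practice does. It is a worthwhile improvement at little cost, not a flaw that undermines the validation.

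**What to change.** Add to 4.1 and 5.9 one prespecified comparator: the creatinine change (or ratio) from the preoperative value to the first postoperative panel, alone. Evaluate it in the same patients as the score, for the same Stage 2-3 endpoint and over the same time windows.

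Report the AUC difference, score minus creatinine change alone, with its 95% confidence interval, using a method for correlated AUCs such as DeLong; the Mann-Whitney U test named in 5.9 does not take account of two scores being measured in the same patients. Limit any claim of value beyond routine creatinine to what that interval supports, and state in advance that a non-significant difference will not be read as proof of no gain. Say whether this comparison falls under the Bonferroni rule in 5.9.

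Cost: no new data, since both creatinine values are already in 5.6, and no larger sample for the 0.1 difference on which the plan is based. The downsides are one more comparison, low power (about 43-50% for a true gain of 0.016-0.019, less for smaller gains or after a Bonferroni adjustment), and a headline that may look less favourable.

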4.1 Main

- Confirm the usefulness and externally validate the scale.
- Compare this scale with other models of AKI prediction after cardiac surgery: Thakar, Mehta, ISR, Callejas, Leicester, CRATE.

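### The usefulness part of the first main objective has no matching analysis: AUC and a Hosmer-Lemeshow test do not show what acting on the score would achieve

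*Combined protocol and SAP*

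**What the plan says.** Section 4.1 gives the first main objective as "Confirm the usefulness and externally validate the scale". The second main objective is a comparison with six other prediction models.

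The hypothesis in section 3 is narrower. It says that the score "has a good predictive ability for moderate to severe AKI after cardiac surgery in the European population".

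Section 5.9 names the measures: "To study the predictive ability, 2 measures will be studied, the discrimination ability by means of the area under the ROC curve". The second measure is a Hosmer-Lemeshow test, for calibration. For comparing scores it says: "The areas under the ROC curve will be compared using the Mann-Whitney U test".

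The background in section 2 gives the clinical motive: "Identification of patients at risk may facilitate early use of management protocols".

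The documents do not define usefulness, set a criterion for it, or say what value would make predictive ability good. They plan no net benefit, risk threshold, sensitivity, specificity, predictive values or reclassification measure.

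**The concern.** Usefulness stands beside external validation in the objective, and the background ties the score to a decision: which patients receive early management. Whether a score helps such a decision depends on how many true and false positives it produces at the risk level where someone would act, compared with flagging everyone or no one.

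AUC depends only on how patients are ranked, so it does not change if every predicted risk is too high or too low. Hosmer-Lemeshow returns a p-value for misfit. A significant result would not tell the sponsor whether the score is still worth using, and a non-significant result would not show that it is. A conclusion about usefulness drawn from 5.9 as written would therefore rest on no measure of decision consequence, and what counts as useful would be settled after the data are seen.

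**Working it through.** The plan gives no figure for usefulness to reproduce. The check asks whether the two planned measures can separate scores with different decision consequences.

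**Inputs from the protocol (5.7).** Incidence of moderate to severe AKI 9%; 1045 evaluable patients, so 1045 × 0.09 ≈ 94 events.

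**Assumptions.** True risk is logistic with a normal linear predictor of SD 1.3 and an intercept set for 9% incidence, which gives an AUC of 0.80. Predicted odds equal true odds multiplied by 1, 0.5, 2 or 3. Thresholds of 10% and 20% are illustrations only.

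**Formula.** Net benefit = TP/n − (FP/n) × t/(1 − t), where t is the risk threshold. Flagging no one gives 0. Flagging everyone gives 0.09 − 0.91 × t/(1 − t).

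**At t = 20%** (weight 0.20/0.80 = 0.25), per 1000 patients:

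| Predicted odds | TP | FP | Net benefit |
|---|---|---|---|
| Calibrated | 39.0 | 79.6 | 39.0 − 19.9 = +19.1 |
| Halved | 19.8 | 23.4 | 19.8 − 5.9 = +13.9 |
| Doubled | 59.8 | 198.6 | 59.8 − 49.7 = +10.1 |
| Tripled | 70.0 | 298.3 | 70.0 − 74.6 = −4.6 |

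Flagging everyone gives 90 − 910 × 0.25 = −137.5.

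**At t = 10%** (weight 1/9), net benefit is about +38 calibrated, +32 halved, +32 doubled and +24 tripled. Flagging everyone gives 90 − 910/9 = −11.1.

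A separate binormal model with the same AUC and incidence gives +19.4, +14.4, +10.3 and −4.9 at 20%, so the pattern does not depend on the exact risk distribution.

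**What AUC sees.** Multiplying all odds by a constant leaves the ranking unchanged, so the AUC is 0.80 in every row.

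**What Hosmer-Lemeshow sees.** Simulated at n = 1045 with ten groups, 10 degrees of freedom and a 5% level, the test rejects in about 6% of samples when the score is calibrated, about 99% when odds are halved, and over 99% when they are doubled or tripled. The verdict is the same, poor fit, for scores worth about +14, +10 and −5 per 1000 at the 20% threshold. Two of these beat flagging no one and one is worse.

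**The case against.** The strongest reply is that usefulness here simply means predictive ability. The hypothesis is worded that way, 5.9 introduces its two measures under that term, and this is a descriptive observational study that ties no action or threshold to the score. On that reading hypothesis and analysis match, and the defect is one undefined word. This stands in part and is why restricting the objective is an acceptable remedy. It does not remove the gap: the objective lists usefulness in addition to validation, and even the narrow reading has no criterion for good.

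Three stronger readings are tempting, and the documents do not support them.

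- A reader might infer that the first main objective cannot be answered at all. Its external validation part is addressed by discrimination and calibration, even though Hosmer-Lemeshow is a weak calibration summary. The predictors ("perioperative change in serum creatinine and postoperative blood urea nitrogen, serum sodium, potassium, bicarbonate and albumin from the first metabolic panel") and the creatinine and dialysis outcomes are on the variable list in 5.6, so the gap is in the analysis plan, not the data.
- A reader might infer that a badly miscalibrated score would pass unnoticed behind a good AUC. The rejection rates above contradict this. For a smaller error that the test usually misses (odds 1.25 times too high, about 10% rejection), net benefit hardly moves: 38.3 to 37.5 per 1000 at a 10% threshold and 19.3 to 18.3 at 20%.
- A reader might infer that the score is useful only if it has the highest net benefit at every threshold. That confuses useful with best, and ranking the scores belongs to the second main objective. It is also a noisy rule: in simulation at n = 1045, a score with true AUC 0.80 was highest at every threshold from 5% to 20% against a single comparator of about 0.78 in only 37% of samples.

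**Conclusion.** The point holds for the usefulness part of the first main objective. That part is undefined and has no matching analysis. The planned measures can show whether the score ranks patients well and whether its risks fit, but not the direction or size of any misfit or whether the score still helps a decision.

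In the illustration, the three miscalibrated scores that the plan would label identically differ by about 19 net true positives per 1000 at a 20% threshold (+14 against −5). This rests on the protocol's 9% incidence and on assumed values for the AUC, the miscalibration factors and the threshold. The negative result needs both threefold over-prediction and the 20% threshold; at 10% every case shown beats flagging everyone and flagging no one. The figures show what the plan cannot distinguish. They do not predict how the score will perform in Europe.

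This should be corrected because a main objective is affected and the remedy is cheap.

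**What to change.** Add decision-curve analysis to 5.9.

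1. Report net benefit with bootstrap 95% confidence intervals for the index score, for each comparator that yields a predicted risk for this outcome (recalibrated where needed), for perioperative creatinine change alone, and for flagging everyone and no one.
2. Use a threshold range that the sponsor sets and justifies before analysis. No single threshold is needed.
3. Base any statement of usefulness on net benefit relative to flagging everyone and flagging no one over that range. Report the comparison with other scores separately under the second main objective, without requiring the index score to be highest throughout.

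If this is not done, restrict the first main objective in 4.1 to external validation of predictive performance.

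**Cost.** One paragraph and a short analysis in R, which 5.9 already plans to use. No new variables are needed, provided that the published score equation, which the documents do not give, can be applied. A threshold range must be agreed in advance, and a usefulness claim becomes harder to make. Precision will also be limited: the standard deviation of net benefit at n = 1045 is about 7 per 1000, so a 95% interval extends roughly 1.96 × 7 ≈ 14 per 1000 either side.

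### The Bonferroni family for the six comparisons in main objective 2 is undefined, and for separate per-model conclusions Holm would give more power at the same family-wise error

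*Combined protocol and SAP*

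**What the plan says.** Section 4.1 has two main objectives. The second is "Compare this scale with other models of AKI prediction after cardiac surgery"; it lists Thakar, Mehta, ISR, Callejas, Leicester and CRATE. Section 4.2 adds, among the secondary objectives, "Assess the performance of other scales and compare them", without naming those scales. The hypothesis in section 3 is only that the index score "has a good predictive ability for moderate to severe AKI after cardiac surgery in the European population".

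Section 5.7 sizes the study on one contrast: "1045 patients are needed to detect a difference of 0.1 in aROC with a power of 80% and an alpha error of 0.05". In section 5.9 the only multiplicity rule is "Bonferroni correction shall be applied for multiple contrasts". It stands after the tests of means and proportions and before the sentences on ROC curves. Of the AUC comparison itself the section says: "The areas under the ROC curve will be compared using the Mann-Whitney U test". No family is defined, and nothing says whether the six comparisons are meant as estimates, as six separate conclusions or as one joint conclusion.

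**The concern.** A main objective with six named comparators produces six index-versus-comparator AUC contrasts. The plan intends significance tests, since it is powered to detect an AUC difference, and it prescribes Bonferroni for multiple contrasts. Two things follow.

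First, the analyst has to decide what the correction divides by: the six contrasts of section 4.1, a larger set that includes section 4.2, or something else. That choice should not be open once the AUCs are known.

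Second, if the six contrasts are the family and each gets its own conclusion, the per-test level is 0.05/6, whereas section 5.7 used 0.05. Some loss of power is the price of controlling family-wise error, but single-step Bonferroni costs more than it needs to. Real differences of the size the study was planned to find would be missed more often than under Holm, with no gain in error control.

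**Working it through.** **Inputs from the plan.** Six named comparators (4.1); AUC difference 0.1, power 80%, alpha 0.05 and 9% incidence (5.7); Bonferroni (5.9). At 9%, 1045 patients give 0.09 × 1045 ≈ 94 events.

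**Assumptions.** Two-sided tests (5.7 does not state sidedness), and equal correlation between the six test statistics. The plan gives no correlation, so a range is shown.

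**The plan's own figure.** 1045 cannot be reproduced from the stated inputs alone, because the reference AUC and the correlation between AUCs are missing. Noether's formula for one Wilcoxon test (AUC 0.6 against 0.5) gives 799 two-sided. Two-AUC formulas give about 210 to 1675, depending on the missing inputs. One combination, Obuchowski's variance with AUCs 0.70 and 0.80 and correlation 0.3, gives 1048. So 1045 is attainable and is not disputed here. The loss allowance is 1045 × 1.1 = 1149.5, rounded to 1150. What follows takes the stated 80% power per contrast as given.

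**Power per model under Bonferroni.**
- 80% power at two-sided 0.05 means the test statistic has mean 1.960 + 0.842 = 2.802.
- Bonferroni over six: 0.05/6 = 0.0083, critical value 2.638.
- Power = Φ(2.802 − 2.638) = Φ(0.163) = 0.565, about 56%.
- Restoring 80% under Bonferroni would multiply N by (2.638 + 0.842)² / 2.802² = 1.54, or about 1612 in place of 1045. This shows the size of the loss; it is not a proposal.

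**Power per model under Holm.** The p-values are ordered and compared in turn with 0.05/6, 0.05/5, 0.05/4, 0.05/3, 0.05/2 and 0.05, stopping at the first failure. Simulation with 400,000 draws gives:

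| Correlation | Bonferroni | Holm, all six differ by 0.1 | Holm, three differ by 0.1 and three by 0 |
|---|---|---|---|
| 0 | 56% | 68% | 60% |
| 0.3 | 56% | 67% | 59% |
| 0.5 | 56% | 67% | 59% |
| 0.7 | 56% | 66% | 59% |
| 0.9 | 56% | 64% | 59% |

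In the last column, power is the average over the three models that truly differ.

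**Where Holm does not help.**
- Showing a difference from at least one model: Holm's first step is the Bonferroni step, so power is identical. At correlation 0.5 it is 90% for both when all six differ by 0.1, and 81% for both when three do.
- Showing a difference from all six: no adjustment is needed, because a false joint claim requires a true null hypothesis to be rejected at 0.05. With all six differing by 0.1 and correlation 0.5, power is 48% with each test at 0.05, 44% with Holm and 19% with Bonferroni.

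**The case against.** The strongest reply is that nothing here is an error. Bonferroni is prespecified and valid. Section 4.1 asks for a comparison, section 3 hypothesises only good predictive ability, and section 5.1 calls the design descriptive. Reporting seven AUCs and six differences with intervals would meet the objective with no win rule. Section 4.2 is already ranked as secondary. All of this stands, and it limits the point to efficiency and an undefined family. It does not remove the point, because section 5.7 powers a test and section 5.9 prescribes both a test and a correction.

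Three stronger readings are tempting and are not supported.

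- *The index score must beat any or all of the six, so the same data support opposite conclusions.* The plan makes no superiority claim. With three true differences and three zeros, at correlation 0.5 under Bonferroni, the score beats at least one model in 81% of trials and all six in under 0.1%. Those figures answer two different questions, and when three models are truly equal, not beating all six is the correct result.
- *The false-positive rate is inflated.* Uncorrected, six contrasts would give a family-wise rate of 27%, 21% or 14% at correlation 0, 0.5 or 0.8, and all 21 pairs of the seven scores would give 43% at 0.5. This requires Bonferroni to be read as excluding the AUC contrasts. The wording has no such restriction, and sentence order is thin evidence for one. The 21 pairs also pool a main with a secondary objective.
- *Holm is better under any rule.* It gains nothing for an at-least-one claim and is not the best choice for an all-six claim.

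**Conclusion.** The point holds as an improvement at almost no cost, not as a flaw that invalidates the analysis. The family for main objective 2 should be defined. For separate conclusions against each named model, Holm controls the same family-wise error as Bonferroni and never rejects fewer hypotheses. The gain is about 9 to 11 percentage points per model (56% to about 65-67%) if all six true differences are 0.1, and about 3 points (56% to about 59%) if only three are.

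These sizes assume two-sided tests, exactly 80% power per contrast at 0.05, and equal correlations of 0.3 to 0.8. They are scenarios, since the plan gives neither reference AUCs nor correlations. That Holm never rejects fewer does not depend on these assumptions. The absence of a success rule is missing detail that one sentence would settle.

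**What to change.** In section 5.9, state that:

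1. The family for main objective 2 is the six AUC differences between the index score and each model named in 4.1, for Stage 2-3 AKI. They are tested with a paired method, because all scores are computed in the same patients.
2. The six p-values are adjusted by Holm instead of Bonferroni. Every difference is reported with its confidence interval, and superiority is claimed only over models with Holm-adjusted p < 0.05.
3. If a joint claim of being better than all six is wanted, it is declared in advance and requires all six tests to be significant, in the index score's favour, at an unadjusted 0.05.
4. Comparisons under 4.2 lie outside this family.

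The cost is SAP wording and one line of analysis code, with no extra patients or data. There are two downsides. Holm has no simple matching simultaneous confidence intervals, so an ordinary 95% interval may exclude zero where the Holm-adjusted p-value is not below 0.05, and the report should say so. The secondary comparisons can no longer be presented as confirmatory.
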